Measures will be collected at an enrollment visit (V1), for both groups. Intervention will begin 0-14 days thereafter for the HCC group. BP and heart rate (HR) recording will be repeated prior to the start of the 7th session for the HCC group. Post-intervention data collections will include an immediate postintervention visit (V2, 1-14 days after intervention completion for HCC, 4-6 weeks after V1 visit for CCC), an intermediate post-intervention visit (V3, primary outcome, 4-6 weeks after intervention completion for HCC, and 8-10 weeks after V1 for CCC), and a final follow up visit (V4, 12-14 weeks following completion of the intervention for HCC, and 16-18 weeks after V1 for CCC). The primary outcome will be differential change in the systolic and diastolic BP from V1 to V3. Following V4, those in the CCC group will be offered an opportunity to receive a course of HCC. Those who accept will have a brainwave assessment 0-14 days before starting sessions and continue to be followed for data collections at 1-7 days (V5), 4-6 weeks (V6), and 12-14 weeks (V7) after completing their HIRREM sessions. Participants will have up to 3 months to crossover. We will utilize linear mixed models (LMMs) to contrast longitudinal changes in systolic and diastolic blood pressure between the HCC and CCC groups. Mean contrasts will be used to compare the changes in blood pressures between groups from V1 to V3, our primary test of efficacy. Additional mean contrasts will be constructed to evaluate the consistency of any benefit of HIRREM through subsequent visits beyond V3. Comparisons of changes in all secondary outcomes will be assessed in a similar fashion.

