Importance: This study will explore the use of HIRREM for the newly defined lower risk sub-category of Stage 1 primary hypertension, a condition now lacking evidence-based therapies in a randomized, clinical trial. The primary outcome, change in blood pressure, is a practical, objective physiological parameter. The objective secondary outcomes evaluating autonomic cardiovascular regulation, may also provide important insights about the importance of the autonomic nervous system, as well as the impact of stress, in this setting. The study will confirm feasibility of a randomized clinical trial using a closed-loop acoustic stimulation intervention in this population, identify any unique challenges for working with this cohort, and provide estimates of effect size, which might justify larger controlled trials. A positive result would suggest that HIRREM may have benefit as a noninvasive, non-drug alternative for initial management of Stage 1 hypertension. The study will also help to identify characteristics of subgroups that might experience differential effects/benefits from HIRREM, and will allow evaluation of any impact on autonomic cardiovascular regulation.

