## Secondary Objectives:

Evaluate whether the use of HCC will result in greater differential changes for a variety of physiological, behavioral, and function outcome measures outlined below, as compared to CCC.

[figure not shown]
- Autonomic nervous system functions, as manifested by heart rate, HRV, and BRS. We expect to see greater changes in autonomic activity and an improvement of sympatho-vagal balance in the HCC group. This would be reflected as changes in heart rate, and an increase of HRV and BRS parameters such as the standard deviation of the R-R interval (SDNN), rMSSD, HF alpha, and Sequence Up, Down, or All.
- 2. Behavioral outcomes such as insomnia (assessed by the Insomnia Severity Index, ISI; Pittsburgh Sleep Quality Index, PSQI; and the Epworth Sleepiness Score, ESS), depression (as assessed by the Center for Epidemiological Studies-Depression Scale, CES-D), anxiety (as evaluated by the GAD-7), traumatic stress (as assessed by the PCL-C), and stress (as assessed by the Perceived Stress Scale, PSS). We expect to see greater improvement in these symptom inventory scores in the HCC group.
- 3. Physical activity recall questionnaire and a short form about satisfaction with current level of physical activity. This will evaluate for any large swings in physical activity level between groups that could influence blood pressure.
- 4. Overall quality of life as evaluated using the QOLS measure. We expect to see greater improvement in overall quality of life scores in the HCC group.
- 5. Functional performance evaluated using drop stick reaction testing. We expect to see more improvement in the HCC group.
- 6. Functional performance evaluated by grip strength, using a hand dynamometer. We expect to see greater improvement of grip strength in the HCC group.
- 7. Impact on comorbidities, for example a history of TBI/concussion, PTSD, ADHD, hot flashes, migraine, or insomnia. We expect to see more reduction of symptoms in the HCC group.

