## Overview:

[figure not shown]
This will be a randomized, single site, pilot clinical trial. Assuming a potential drop-out rate of 20%, up to 24 subjects will be enrolled to achieve a goal of having at least 20 subjects (10 per group) complete the study, per protocol. Participants will be recruited from among patients who have been diagnosed with Stage 1 primary hypertension, based on blood pressures between 130-139 mmHg systolic, and/or 80-89 mmHg diastolic, as documented by their health care providers on two separate occasions during the prior 18 months. This, in the absence of known clinical cardiovascular disease, risk for cardiovascular disease of  $\geq$  10%, or other medical conditions associated with likelihood for development of hypertension, and who have not yet been started on pharmacological treatment.

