Those who have no other exclusions, are interested to participate, and provide informed consent will be randomly assigned to receive 8-16 sessions of in-office acoustic stimulation linked to brainwave activity (HCC), over a maximum of 4 weeks, while continuing their other current clinical care, or to continue their current clinical care alone (CCC). There will be pre- and post-intervention data collection to include systolic and diastolic BP, and many secondary outcome measures including measures of autonomic cardiovascular regulation (continuous recording of BP and HR for calculation of measure of HRV and BRS), behavioral symptom outcomes (ISI, PSQI, ESS, CES-D, GAD-7, PCL-C, PSS), quality of life measure (Quality of Life Scale, QOLS), short physical activity recall (International Physical Activity Questionnaire, IPAQ-SF), and function performance measures (drop stick reaction testing, and grip strength). All measures will be collected at an enrollment visit (V1), for both groups. Intervention will begin 0-14 days thereafter for the HCC group. BP and heart rate (HR) recording will be repeated prior to the start of the 7th session for the HCC group. Post-intervention data collections will include an immediate postintervention visit (V2, 1-14 days after intervention completion for HCC, 4-6 weeks after V1 visit for CCC), an intermediate post-intervention visit (V3, primary outcome, 4-6 weeks after intervention completion for HCC, and 8-10 weeks after V1 for CCC), and a final follow up visit (V4, 12-14 weeks following completion of the intervention for HCC, and 16-18 weeks after V1 for CCC). The primary outcome will be differential change in the systolic and diastolic BP from V1 to V3. Following V4, those in the CCC group will be offered the opportunity to receive a course of HCC, and those who accept will have up to 3 months to schedule a brainwave assessment 0-14 days before starting sessions and continue to be followed for data collections at 1-14 days (V5), 4-6 weeks (V6), and 12-14 weeks (V7) after completing their HIRREM sessions.

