Interested subjects will be informed with a more detailed description of the study, and the extent of their commitment, through phone calls or email communications. If no exclusions are apparent from initial phone or email communications, potential participants will complete an online eligibility screening form, which will be reviewed by the study team. If potential participants express continued interest in the project and have no major exclusions, and after receipt of BP and cholesterol testing documentation as noted above, the cardiovascular risk will be calculated. If confirmed that they have < 10 % risk for cardiovascular disease, they will be scheduled for an enrollment visit (V1) at which time an informed consent will be completed. As part of the informed consent process, study procedures, schedule for visits, and duration of participation will again be reviewed, and alternatives discussed, including the option to not enroll in this project, and follow up with their primary health care provider.

After informed consent is obtained, a blood pressure will be obtained to confirm eligibility. Those with BP less than 130 mmHg systolic or 80 mmHg diastolic, or systolic BP  $\geq$  140 mmHg systolic, or  $\geq$  90 mmHg diastolic, will be considered as screening failures, and will not move on to the remaining enrollment visit activities. For those confirmed to have an eligible baseline blood pressure reading, a brief medical history will be obtained, randomization will be completed, and baseline study measures obtained, prior to the start of the intervention, or continuation of current care. Those scheduled for an enrollment visit will also be provided a copy of Appendix B, Handout to Study Participants, and/or a welcome email with details. Prior to randomization, women of childbearing potential will also have a urine pregnancy test performed at the WFBH Outpatient Laboratory, 2nd floor, Piedmont Plaza 1 Building. If positive, they will be excluded from the study.

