## Statistical Analysis:

Continuous variables will be summarized with standard descriptive statistics, such as quartiles, means, and standard deviations, while categorical variables will be summarized with percentages and frequencies. LMMs will be employed to contrast longitudinal changes in systolic and diastolic blood pressure between the HCC and NCC groups. Mean contrasts will be used to compare the changes in blood pressure between groups from V1 to V3, our primary test of efficacy. Comparisons of changes in all secondary outcomes will be assessed in a similar fashion. Assumption and computation diagnostics will be assessed for all model fits (Cheng J, et al., 2010), and model adjustments and outcome variable transformations will be made as necessary. Data will be analyzed using SAS v9.4 (SAS Institute, Inc., Cary, NC) or the R Statistical Computing Environment.

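### How V1 enters the mixed model is left open; adjusting for it could modestly tighten the symptom and quality-of-life estimates if pre/post correlation is moderate, but not the primary BP estimate

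*Combined protocol and SAP*

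**What the plan says.** The Statistical Analysis section plans linear mixed models and states: "Mean contrasts will be used to compare the changes in blood pressure between groups from V1 to V3, our primary test of efficacy". It adds: "Comparisons of changes in all secondary outcomes will be assessed in a similar fashion". The Abstract repeats the primary test ("Mean contrasts will be used to compare the changes in blood pressures between groups from V1 to V3, our primary test of efficacy"), and the Overview defines the endpoint the same way: "The primary outcome will be differential change in the systolic and diastolic BP from V1 to V3". The Secondary Objectives apply the idea of differential change broadly: "Evaluate whether the use of HCC will result in greater differential changes for a variety of physiological, behavioral, and function outcome measures".

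None of these places says whether V1 is a response with a separate mean in each arm, a response with one mean shared by both arms, or a covariate. Covariance structure and degrees-of-freedom method are not given either. The same section allows model adjustments and transformations as diagnostics require.

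On size, the Overview says: "Assuming a potential drop-out rate of 20%, up to 24 subjects will be enrolled". The aim is about 10 completers per arm. The Abstract wants the pilot to "provide estimates of effect size, which might justify larger controlled trials".

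On timing, the eligibility BP is read after consent and before randomization (Participants/Subjects). The other baseline measures are listed after randomization in that section, and after participants learn their group in the Enrollment Visit section.

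**The concern.** With free group-by-visit means and complete data, the V3 contrast from the planned model is the plain difference in mean change. That estimate keeps the full noise of V1. A baseline-adjusted estimate removes part of it whenever the regression of follow-up on baseline has a slope clearly below 1. With about 10 per arm and a stated aim of estimating effect sizes, precision given away on scales already collected at V1 matters a little.

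Two things sharpen the point. First, the choice could be made after the data are seen. Second, the adjustment that gains most assumes V1 is unaffected by allocation, yet in this open comparison the self-reported scales are completed after participants are told their group. The order of the V1 visit therefore decides how secure any handling of V1 is.

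**Working it through.** **Inputs.** From the documents: 20 completers, about 10 per arm, 20% dropout, 24 enrolled; pilot SDs in Tables 1 and 2; the V1 BP entry ranges. Not in the documents, hence assumed: the pre/post correlation r, equal SDs at V1 and V3, and BP residual SDs and reliability.

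**The plan's own figure.** 20 × 1.2 = 24, as stated. Dividing by the retention rate gives 20/0.8 = 25, and 24 × 0.8 = 19.2, so about 10 per arm is a fair basis.

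**Closed form, equal SDs, n per arm.**
- Variance ratio, change contrast over adjusted estimate = [2/(1+r)] / [1 + 1/(2n−4)]. At n = 10 the divisor is 1 + 1/16 = 1.0625.
- CI width ratio, adjusted over change = √((1+r)/2) × √1.0625 × (t₁₇/t₁₈) = √((1+r)/2) × 1.035.
- Example, r = 0.5: 0.866 × 1.035 = 0.896, or 10.4% narrower.

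The last two columns simulate the mixed model itself (four visits, exchangeable true correlation, unstructured REML, Kenward-Roger), comparing a common V1 mean with free means. In the dropout case 12 per arm are enrolled and 2 per arm are lost before V3.

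| r | Variance ratio | CI narrower, closed form | Simulated, complete data | Simulated, dropout |
|---|---|---|---|---|
| 0.3 | 1.448 | 16.5% | 17.5% | 14.8% |
| 0.5 | 1.255 | 10.4% | 11.5% | 9.5% |
| 0.7 | 1.107 | 4.6% | 5.7% | 4.8% |
| 0.8 | 1.046 | 1.8% | not run | not run |
| 0.88 | 1.001 | −0.4% | 0.8% | 0.7% |

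A separate simulation of covariance analysis against change scores gave 10.6%, 4.9% and 2.1% at r = 0.5, 0.7 and 0.8. Type I error of the constrained mixed model was 0.051–0.056, against 0.046–0.053 for free means. The closed form is therefore the safer guide.

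**Pilot slopes, symptom scales (Table 2).** Slope = (s₀² + s₁² − s_change²) / (2s₀²).
- ISI: (51.84 + 10.24 − 21.16)/(2 × 51.84) = 0.39
- GAD-7: (14.44 + 5.76 − 18.49)/(2 × 14.44) = 0.06
- CES-D: (136.89 + 14.44 − 96.04)/(2 × 136.89) = 0.20

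All are well below 1, but they come from one open-label arm of 10. The printed p-values for GAD-7 (0.06) and CES-D (0.07) do not follow from the printed changes and SDs by paired t-test (0.005 and 0.041). They are illustrative only.

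**Primary BP.** A uniform 10 mmHg band has SD 10/√12 = 2.9. With slope 0.5 and residual SD 8, the large-sample width ratio is 8/√(64 + 2.9² × 0.5²) = 0.984; × 1.035 = 1.019, or 1.9% wider after adjustment. If the entry rule lets the V1 SD reach 6, it is 8/√(64 + 36 × 0.25) = 0.936; × 1.035 = 0.969, or 3.1% narrower.

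The spread depends on the entry rule, which is stated in two ways. Participants/Subjects fails "Those with BP less than 130 mmHg systolic or 80 mmHg diastolic". The Enrollment Visit section fails only those low on both components. Simulated variance ratios were 0.94–1.00 under the former and 0.97–1.12 under the latter. For SBP at an assumed reliability of 0.65, the half-width goes from 8.50 to 8.66 mmHg and from 8.72 to 8.66 mmHg respectively.

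**Autonomic measures.** Taking the treated slope from the pilot tables, and assuming controls keep the baseline SD with r 0.5–0.8, variance ratios are 0.94–0.97 for Table 1 Up SBP (a loss), 0.96–1.02 for SDRR and rMSSD, 0.97–1.02 for HF alpha, 1.01–1.11 for Table 3 sequence BRS and 1.07–1.17 for Table 3 SDNN.

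**Learning the group before V1 scales.** Suppose this shifts V1 by 0.2 SD, with slope 0.5. If the shift is at V1 only, the change contrast is off by 0.20 SD and the adjusted one by 0.5 × 0.2 = 0.10. If it persists to V3, the errors are 0 and 0.2 − 0.10 = 0.10.

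**The case against.** The strongest reply is that nothing here is wrong. The free-means contrast is unbiased with nominal type I error, a common-V1-mean model also fits the plan's wording, and the pilot has no power or precision target to miss. That stands: this is an efficiency choice left open. A reader might infer that the planned contrast is invalid or biased; the documents do not support that.

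A reader might also infer a fixed saving of 5–10% on every symptom scale. That range needs r of about 0.5–0.7. The documents give no control-arm correlation for any scale, and nothing from which to compute one for PSQI, ESS, PCL-C, PSS or QOLS. Nor do the pilot SDs establish a larger gain. Combined with an assumed stable control arm they give 19–25%, but from a single treated group of 10 with internally inconsistent p-values.

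Imposing one constrained model on every outcome is not supported either. It gains about nothing for BP and may lose slightly there and for some autonomic measures.

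Finally, the constraint is least secure for self-reported scales under the present visit order. A persisting 0.2 SD shift would cost the adjusted estimate 0.10 SD, more than the half-width saved at r = 0.5 with dropout (0.903 − 0.817 = 0.086 SD). This stands, and it is why the visit order must change along with the model. The change contrast is not immune: it does worse if the shift is confined to V1.

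**Conclusion.** The point holds as a matter of efficiency and prespecification. V1 handling is unspecified, and on one natural reading the contrast is an unadjusted difference in change. For the symptom and quality-of-life scales the gain from adjustment ranges from about 10% of CI width to nothing as r rises from 0.5 to about 0.88, assuming equal SDs and 10 per arm. Pilot slopes suggest a gain is likely but cannot size it.

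For the primary BP contrast the effect runs from a few percent wider to a few percent narrower, depending on the entry rule and the assumed V1 spread. A reader might infer that the primary test loses power through this omission; the restricted V1 range means no such claim can be made. Worth considering, with medium confidence because r is assumed.

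**What to change.** 1. In Participants/Subjects and Enrollment Visit, place all V1 outcome measures (questionnaires, autonomic recording, reaction time, grip strength, brainwave assessment) before group assignment is notified.
2. In Statistical Analysis, prespecify for the symptom and quality-of-life scales a mixed model with a common V1 mean (or V1 as covariate), separate arm means at V2 to V4, unstructured covariance, REML and Kenward-Roger degrees of freedom. Report the V3 difference with a 95% CI. Give the free-means change contrast as a sensitivity analysis, particularly for any measure already collected after notification.
3. For BP and the autonomic measures, name one V1 handling in advance. Either is acceptable; precision is not the reason.
4. Reconcile the two statements of the low-BP screen-failure rule.

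The cost is analysis-plan wording and a reordered V1 visit; no new data are needed. Statistically, where the slope is near 1, adjustment inflates variance by about 6% at 10 per arm (1/16), and the constrained model's type I error sits slightly above nominal.

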# Participant Compensation:

Participants will receive up to \$100 compensation for time, travel, and inconvenience related to study visits. Subjects who do not complete the entire study will receive a prorated portion of this amount (\$25 per visit for completion of each of four data collection visits). Participants whose initial BP is too low, or too high to meet criteria Stage 1 hypertension, and are thus considered screen failures, and do not complete the rest of the at the enrollment visit, will receive a \$10 gift card as compensation for their time.

# Human Subjects Protection:

## Consent:

Written informed consent will be obtained by the research staff from each competent subject.

## Confidentiality and Privacy:

Confidentiality will be protected by collecting only information needed to assess study outcomes, minimizing to the fullest extent possible the collection of any information that could directly identify subjects, and maintaining all study information in a secure manner. Per institutional policy, all research study participants will be assigned a hospital MRN number, if none already exists. To help ensure subject privacy and confidentiality, only a unique study identifier number, and first name will appear on the data collection form. Any other collected patient identifying information corresponding to the unique study identifier will be maintained on a separate master log. The master log will be kept secure, on a separate, limited access user group on a shared network drive, with access limited to designated study personnel. Following data collection subject identifying information will be destroyed at the earliest opportunity, consistent with data validation and study design, producing an anonymous analytical data set. Data access will be limited to study staff. Data and records will be kept locked and secured, with any computer data password protected. No reference to any individual participant will appear in reports, presentations, or publications that may arise from the study.

Brain State Technologies, LLC (BST) may assist with brain pattern analysis. To accomplish this, BST is provided with the first 8 characters from the randomly generated, 36 character identifier that the HIRREM software generates for each participant's brain frequency and amplitude data, along with the participant's age and gender, which are believed important for understanding brain patterns. No other participant-specific information is provided.

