prehypertension (Chen S, et al., 2016; Lin G, et al., 2012; Wang S, et al., 2010; Xu XY, et al. 2007). Passive listening to Indian music, along with lifestyle modifications has also been reported to lower BP and improve autonomic function in subjects with prehypertension/Stage 1 hypertension (Kunikullaya KU, et al., 2015). Strategies that more directly target/influence central management of autonomic cardiovascular regulation may thus be expected to have beneficial effects on downstream autonomic function, as well as blood pressure in this cohort.

High-resolution, relational, resonance-based, electroencephalic mirroring (HIRREM®) was developed by Brain State Technologies, Scottsdale, AZ. It is a noninvasive, electroencephalic-based method to facilitate client-unique relaxation and auto-calibration of cortical neural oscillations by reflecting auditory tones in near real time (Gerdes L, et al., 2013). HIRREM uses scalp sensors to observe brain frequencies and amplitudes in real time, and software-guided algorithmic analysis to identify and translate selected brain frequencies into audible tones to support real-time self-optimization of brain activity. The audible tones are reflected back to the recipient bilaterally, simultaneously, in 4-8 milliseconds, providing an opportunity for the recipient to, figuratively speaking, listen to the song the brain is playing right now. Although exact mechanisms await confirmation, it appears that with rapid updating regarding its own electrical activity, intended to support frequency-matching or resonance between the acoustic stimulation and oscillating brain networks, the brain is supported towards autocalibration, and self-optimization. As a closed-loop process, no conscious or cognitive activity is required, yet the brain pattern is observed to shift on its own terms towards improved balance, and often reduced hyperarousal.

Functionally, it may be that this acoustic stimulation facilitates kindling of sleep in neuronal units, which had previously been stuck in the "on" position due to stress responses (Krueger JM, et al., 2013). Better sleep is foundational for overall health and healing. A key aspect of observed beneficial effects may also be related to the observed improvement in downstream autonomic function, as evidenced by increased heart rate variability and baroreflex sensitivity, apparently associated with increased dynamic range and flexibility of autonomic responses managed by the brain.

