# High-resolution, relational, resonance-based, electroencephalic mirroring (HIRREM):

High-resolution, relational, resonance-based, electroencephalic mirroring (HIRREM®) is a computerbased technology created by Brain State Technologies, LLC, Scottsdale, AZ, designed to support relaxation and auto-calibration of neural oscillations through reflecting back audible tones in near real time.

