# Brainwave Assessment:

This is the first step in the HIRREM process. It occurs during the V1 enrollment visit, and will be performed on both groups. The assessment creates a map of frequencies and amplitudes, and informs the choice of protocols for the initial HIRREM sessions. Our pilot data also suggest that this information

is also useful for correlating with autonomic function (HRV and BRS), and that changes can be observed in frequencies and amplitudes from pre- to post-HIRREM. For the assessment, with the participant in a sitting position, sensors are sequentially placed over six areas of the scalp to record one minute epochs of data while the brain is at rest, or on task, with eyes open and with eyes closed. For the assessment, measurements are taken at homologous regions of the bilateral hemispheres according to the 10-20 International System at F3/F4, C3/C4, P3/P4, T3/T4, FZ/OZ, and O1/O2 with both eyes closed (EC; one minute), and eyes open (EO; one minute) conditions ("Report of the committee on methods of clinical examination in electroencephalography: 1957," 1958). For EO assessments, subjects are given standardized tasks involving numerical digit recall (F3/F4), reading silently (C3/C4), math calculations (P3/P4), listening comprehension (T3/T4), and to relax with eyes open (O1/O2). A sixth midline measurement is taken at FZ/OZ, with an EO task to count number of appearances of a specific word as they read a standardized printed passage, with additional recordings at a seventh (FP1/FP2, given standardized tasks involving numerical digit recall), and eighth (CB1/CB2, relax with eyes open) location. The reference sensors are connected at A1/A2 and linked for assessments. The data are processed to identify patterns and imbalances of frequencies and amplitudes, which are used to generate specific protocols for the initial HIRREM session. The assessment takes about 30-45 minutes to complete. An assessment will be repeated at the V3 visit to allow comparison between brain patterns at baseline, and post-intervention, between the two groups.

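### The HIRREM developer may assist with brain-pattern analysis under a participant-level software identifier, and nothing in the protocol masks that work to arm or visit

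*Combined protocol and SAP*

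**What the plan says.** The Brainwave Assessment section has both groups assessed at V1 and states the purpose of the repeat: "An assessment will be repeated at the V3 visit to allow comparison between brain patterns at baseline, and post-intervention, between the two groups". The visit schedule adds an assessment at V4 and none at V2.

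The Background says that HIRREM "was developed by Brain State Technologies, Scottsdale, AZ". The Confidentiality and Privacy section then says: "Brain State Technologies, LLC (BST) may assist with brain pattern analysis". For that purpose "BST is provided with the first 8 characters from the randomly generated, 36 character identifier that the HIRREM software generates". There is one such label per person, and the section attaches it to that person's "brain frequency and amplitude data"; age and gender are supplied too. It closes the topic with: "No other participant-specific information is provided". The preceding paragraph of the same section also says: "Data access will be limited to study staff".

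None of these sections, nor Statistical Analysis or Data and Safety Monitoring, says that whoever works on brain patterns is kept unaware of arm or visit.

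**The concern.** The company that developed the intervention has an evident interest in the result, and the protocol allows it to help with brain-pattern analysis. The label it works under is made by its own software and belongs to the participant, not to a single recording. Such a label protects privacy but does not mask: it shows which recordings come from the same person, and it may lead to other records that reveal treatment.

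This matters because the brain-pattern analysis is not specified. If measures are derived or chosen by someone who can tell arm or visit, the between-group difference can be favoured without anyone noticing. Brain pattern is the trial's only direct measurement of the brain, and the pilot-data section argues for a centrally mediated effect, so readers may be inclined to use this comparison as support for a mechanism.

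**Working it through.** No power or sample-size figure is involved. The check sets the sections side by side.

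1. **Is a between-group comparison planned?** Yes, baseline to V3 (Brainwave Assessment).

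2. **What is the developer's role?** Optional assistance with brain-pattern analysis (Confidentiality and Privacy). The section does not say whether that includes the between-group comparison.

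3. **What does it receive?** Part of the software identifier, age and gender. Arm and visit are not listed. Nor are recordings, yet patterns cannot be analysed without them, so which recordings the developer sees is left open.

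4. **Does the identifier link visits?** Yes. It is generated per participant, so V1 and V3 recordings from one person carry the same label. Telling which came first also needs dates or visit labels, and the text is silent on both.

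5. **Could it reveal arm?** Only if session records are visible under it. By V3, per HCC participant (HIRREM Sessions):
   - minimum: 8 sessions × 3 protocols = 24 protocol runs
   - maximum: 16 sessions × 10 protocols = 160 protocol runs
   - per CCC participant: 0, because HIRREM is offered only after V4

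   These counts show how plain the signal would be if it were visible. They do not measure bias.

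6. **Are session records kept and linked to the person?** This is an inference. The HIRREM Sessions section says that frequencies and amplitudes are monitored during sessions and that technologists draw on session data when choosing protocols. The figure legend under Specific Relevant Pilot Data sets one participant's baseline beside a minute from the 15th session, so session data were kept and matched to baseline in earlier work. No section says that in this trial they share the identifier or can be seen by the developer.

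7. **Does timing matter?** Yes. Once CCC participants cross over, they have sessions too, and the presence of sessions no longer separates the arms. Dates would, since HCC sessions precede V3 and crossover sessions follow V4. Dates can also inform by themselves: V3 falls 8 to 10 weeks after V1 in CCC, but up to 2 + 4 + 6 = 12 weeks after V1 in HCC (start delay, session period, V3 window).

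8. **Is replacing the identifier enough?** Not with exact age and gender attached. Among at most 24 people, that pair could often single out a person and relink the recordings.

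9. **How much is left to choose?** Recording is well specified: 8 locations × 2 eye states = 16 one-minute epochs per assessment. The summary is not: Statistical Analysis names no brain-pattern measure, and the Brainwave Assessment section does not say which locations, bands or indices will be compared.

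10. **Can the bias be sized?** No. The documents give no brain-pattern measure, variance or expected difference.

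**The case against.** The case against is substantial. The assistance is optional. It may not concern the outcome comparison at all: the HIRREM Sessions section describes ongoing review of brain patterns to guide treatment, and the Safety section mentions the developer's case management support, where masking has no place. The list of items supplied excludes arm and is expressly closed, and general data access is confined to study staff. Both groups are assessed, so holding an identifier does not mark a participant as HCC. Crossover further blurs what the presence of sessions means. Finally, brain pattern is neither the primary outcome nor one of the seven secondary objectives.

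Most of this stands, and it limits the point. A reader might infer that the developer runs the analysis, that the identifier covers the session data, and that arm can therefore be read for every participant. The documents support none of the three: the role is to assist, coverage of sessions is not stated, and arm could be inferred only under the conditions in steps 5 and 7. Nor does any section hand the choice of measures to the developer.

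What the objection does not remove is the missing safeguard. The closing sentence on participant-specific information is a privacy limit. It keeps arm off the list, but it does not stop arm being inferred from records reached through the identifier, and it does not unlink the visits. Limiting access to study staff does not mask anyone either. The text on brain-pattern analysis has no exception for the between-group comparison.

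**Conclusion.** The point holds in a limited form. The protocol plans a between-group comparison of brain patterns and allows the developer to assist with brain-pattern analysis under an identifier that links a person's recordings across visits, with no masking to arm or visit. That much is in the text. That the developer could infer arm rests on two assumptions: that its assistance extends to this comparison, and that session records are visible under the identifier, with the work done before crossover or with dates visible.

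The reach is an exploratory comparison in a pilot of up to 24 people. The primary outcome is blood pressure from an automated device and is not affected. The size of any bias cannot be given. The change is worth making because it is cheap and removes a doubt that could not be resolved afterwards.

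**What to change.** Amend the Confidentiality and Privacy section for any developer help with the between-group comparison:

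- Send only assessment recordings, each assessment under its own new random code made by the study team.
- Remove the software identifier, dates (including file dates), visit, arm and all session files.
- Give age in broad bands, or withhold it, alongside gender, so that recordings cannot easily be relinked.
- Have the developer return derived values per recording. The study team locks them, then links them to participant, visit and arm and makes the between-group comparison.
- State that any developer support during HIRREM sessions is separate and unaffected.

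Cost: one paragraph of protocol text and recoding of up to 24 participants × 3 assessments (V1, V3, V4) = 72 assessments, plus any pre-crossover assessments if those are sent. The documents do not say how easily the software identifier and file dates can be stripped, so this should be tried on a test file first. The downside is that the developer cannot view a person's sequence of recordings or exact age while deriving values.
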